3.1.2 Neoadjuvant Cohort

The primary objective of the neoadjuvant cohort is to evaluate the safety and tolerability of neoadjuvant nivolumab administration in subjects with select tumor types.

For subjects in the neoadjuvant cohort, radiographic tumor assessments will occur at the following time points (see [Table 5.4.1-2](#)).

- Screening to ensure the subject has resectable disease.
- Within 7 days and prior to the planned surgery or chemotherapy/radiation
- Post-surgery (SCCHN, MCC, Gyn) or post-chemotherapy/radiation (Gyn cohort when appropriate) at indicated Follow-Up visit times.

All subjects must have tumor amenable to pre-treatment biopsy (core needle); post-treatment biopsy will consist of the operative specimen or core needle biopsy for the cervical/vaginal/vulvar subjects.

Treatment within the **neoadjuvant** cohort will consist of:

- A pre-treatment, core-needle, biopsy for all subjects. (Four core-needle biopsies, as described in the laboratory manual, are suggested.)
- Two doses of nivolumab will be administered at 240 mg IV on Day 1 and Day 15
- Surgical resections (SCCHN, MCC, Gyn), or biopsy followed by chemotherapy/radiation (where appropriate for Gyn patients only) will occur on Day 29 (\pm 7 days). No other pre-surgical therapy is allowed.
- After neoadjuvant nivolumab treatment followed by surgical resection or biopsy, subjects will receive standard of care (observation, chemo and/or RT, according to physician's choice).
- Subjects who develop unresectable recurrent or metastatic disease within 1 year of surgery or chemotherapy/radiation completion may receive nivolumab at 240 mg IV every 2 weeks until 24 months of treatment, toxicity, or disease progression, if medically eligible, ie, meet eligibility criteria for metastatic cohort. Written approval from the sponsor's medical monitor is required for subject to be considered eligible. Nivolumab can be administered no earlier than 4 weeks after the last standard of care treatment.

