3.3 Exploratory

3.3.1 Neoadjuvant Cohort

- To determine the percent change from baseline of immune cells and the percent change from baseline of select immune activation/inhibitory molecules of viral-specific T cells in tumor specific subsets of nivolumab treated subjects.
- To evaluate the recurrence-free survival after neoadjuvant administration of nivolumab and surgery
- To determine the percent change from baseline in tumor volume after two doses of neoadjuvant nivolumab.

- To determine pathologic complete response of tumors in subjects who receive surgical resection after two doses of neoadjuvant nivolumab in SCCHN, resectable Merkel Cell Carcinoma, and cervical, vaginal, or vulvar cancer.
- To evaluate changes in anti-viral and anti-tumor immune responses at the tumor site, using proliferative and/or functional assays.
- To investigate the potential association between selected biomarker measures in peripheral blood and tumor tissue, including PD-L1, with safety and clinical efficacy measures.
- To investigate the pharmacodynamic activity of nivolumab in the peripheral blood and tumor tissue as measured by gene expression, flow cytometry, immunohistochemistry and soluble factor assays.
- To study the effect of nivolumab on the viral antigen specific T cell responsiveness in the peripheral blood.
- To evaluate the potential association between the number of tumor mutations and neoantigens with clinical efficacy measures and determine if tumor antigen-specific T cells are present in the periphery.
- To assess the subject's overall health status as assessed by the EQ-5D.
- To evaluate cancer specific health related quality of life as assessed by EORTC QLQ-C30.
- To characterize pharmacokinetics of nivolumab and explore exposure-response relationships.
- To characterize the immunogenicity of nivolumab.

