- The percent change in tumor volume from baseline after two doses of neoadjuvant nivolumab is defined as the ratio of the change in tumor volume and the baseline tumor volume.
- The proportion of treated subjects who experiences pathologic complete response will be used to determine pathologic response rate of tumors after two doses of neoadjuvant nivolumab in HPV positive and negative SCCHN, resectable Merkel Cell Carcinoma, and HPV positive

cervical, vaginal, or vulvar cancer. Pathological complete response (pCR) is defined as the absence of residual invasive cancer on hematoxylin and eosin evaluation of the complete resected tumor specimen and all sampled regional lymph nodes following completion of neoadjuvant systemic therapy.

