5 SAMPLE SIZE

Sample size determination is not based on statistical power calculation.

1) Neoadjuvant Cohort:

The SCCHN tumor types will contain 21 HPV-positive and 21 HPV-negative evaluable subjects. MCC and HPV positive cervical, vaginal, or vulvar cancers tumor types will contain 21 evaluable subjects each. A sample size of 21 can detect, with more than 66% and 89% probability, a safety event that occurs at an incident rate of 5% and 10%, respectively. Assuming 10%, 15%, and 20% for pathologic complete response rate, a sample size of 21 can detect, more than 89%, 97% and 99% probability, at least one pathologic complete response respectively.

1) Recurrent/Metastatic Monotherapy Cohort:

HPV+ SCCHN, GYN, MCC and NPC tumor type in the recurrent/metastatic cohort will contain 23 subjects. Table 5-1 shows the probabilities of observing 0, 1 or 2 responders and \square 3 responders assuming 5%, 20% and 30% true response rate of ORR. shows the two sided 95% exact CI using Clopper-Pearson methods based on observed 3, 4 and 5 responders out of 23 subjects.

EBV+ Gastric tumor type will contain approximately 12 subjects, due to the low prevalence. Table 5-3 shows the precision of the estimation of ORR based on the two-sided 95% exact CI using Clopper Pearson methods based on 1, 2, 3, 4 and 5 responders out of 12 subjects. Assuming the

true ORR is 25%, 12 subjects can provide approximately 84% probability to observe at least 2 responders.

Table 5-1: Probability of observing responses given true ORR for sample size of 23 subjects

True ORR	Probability of observing 0,1 or 2 responses	Probability of observing ≥ 3 responses
5%	89.5%	10.5%
20%	13.3%	86.7%
30%	1.6%	98.4%

Table 5-2: Two-sided 95% exact CI using Clopper-Pearson method based on number of observed responses out of 23 subjects

The number of observed responses	3	4	5
Observed Response Rate	3/23 (13.0%)	4/23 (17.4%)	5/23 (21.7%)
95% exact CI	(2.8%, 33.6%)	(5.0%, 38.8%)	(7.5%, 43.7%)

Table 5-3: Two-sided 95% exact CI using Clopper-Pearson method based on the number of observed responses out of 12 subjects

Number of observed responses	1	2	3	4	5
Observed Response Rate	1/12 (8.3%)	2/12 (16.7%)	3/12 (25.0%)	4/12 (33.3%)	5/12 (41.7%)
95% exact CI (%)	(0.2, 38.5)	(2.1, 48.4)	(5.5, 57.2)	(9.9, 65.1)	(15.2, 72.3)

2) Recurrent/Metastatic Combination Cohort:

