6.3.2 Analysis Populations

Within each tumor type in each cohort the following populations will be defined.

- **Enrolled subjects:** All subjects who signed an informed consent form and were registered into the IVRS.

- **Treated subjects:** All subjects who received at least one dose of nivolumab. This is the primary population for efficacy and safety analyses.
- **Response evaluable subjects:** All treated subjects who have a BOR of CR, PR, SD, Non-CR/Non-PD or PD, and target lesion(s) assessed at baseline, and one of the following: i) at least one on-study timepoint (before sub-sequent therapy) with all baseline target lesion(s) assessed; ii) clinical progression or death before any on-study tumor assesment.
- **Evaluable neoadjuvant subjects:** All treated subjects in neoadjuvant cohorts (N-1, N-2, N-3, N-4) who have available paired tissue samples at screening and Day 29.
- **Pathologic response evaluable subjects:** All treated subject in neoadjuvant cohorts who received study treatment surgery and have known pathological response based on Day 29 TN classification.
- **Outcomes research subjects:** All treated subjects who have an assessment at baseline and at least one post baseline assessment.
- **Pharmacokinetic subjects:** All treated subjects have available serum concentration data.
- **Immunogenicity subjects:** All treated subjects with baseline and at least 1 post baseline immunogenicity assessment.
- **PD-L1 tested subjects:** All subjects who had a tumor tissue sample available for assessment of PD-L1 expression at baseline.
- **Treated PD-L1 tested subjects:** All PD-L1 tested subjects who received at least one dose of study treatment.
- **PD-L1 evaluable subjects:** All treated PD-L1 tested subjects with quantifiable PD-L1 expression.

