7 STATISTICAL ANALYSES

7.1 General Methods

Unless otherwise noted, the following subsections describe tabulations of discrete variables, by the frequency and proportion of subjects falling into each category. Percentages given in these tables will be rounded and, therefore, may not always sum to 100%. Continuous variables will be summarized using the mean, standard deviation, median, minimum and maximum values. If a missing category is not being presented in the data display, only those subjects with non-missing values for the parameter being assessed are included in the percentage calculation.

Time to event distribution (e.g. progression free survival, overall survival, time to response, and duration of response) will be estimated using Kaplan Meier techniques. When appropriate, the median along with the corresponding log-log transformed 95% CI will be estimated. Rates at fixed time points will be derived from the Kaplan Meier estimate and corresponding confidence intervals will be derived based on Greenwood formula³ for variance derivation and on log-log transformation applied on the survivor function $S(t)$ ⁴.

Confidence intervals for binomial proportions will be derived using the Clopper-Pearson method⁵.

All analyses will be performed separately for each tumor type upon completion of follow-up for the primary endpoint in each tumor type. Safety analyses will also be performed for each tumor type.

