7.5.3 Exploratory Analyses

7.5.3.1 Neoadjuvant Cohort only

- The percent change from baseline of immune cells and the percent change from baseline of select immune activation/inhibitory molecules of viral-specific T cells in tumor specific subsets of treated subjects will be evaluated. Change from baseline will be summarized using descriptive statistics (n, mean, standard deviation, median, first and third quartiles, minimum, maximum).
- The following analyses will be conducted for RFS in primary analysis and sensitivity analysis. RFS curves for each tumor type will be estimated using the Kaplan-Meier (KM) product limit method. Median RFS and the corresponding two-sided 95% confidence intervals using the log-log transformation will be computed. Survival rates at 3, 6, 9, 12 months will be estimated using KM estimates on the RFS curve for each tumor type. Minimum follow-up must be longer than the time point to generate the rate. Associated two-sided 95% CIs will be calculated. Primary RFS analysis should use censoring scheme listed in [Table 4.3-1](#). Sensitivity RFS analysis should use censoring scheme listed in [Table 4.3.1-2](#).
- The percent change in tumor volume from baseline after two doses of neoadjuvant nivolumab will be summarized using descriptive statistics (n, mean, standard deviation, median, first and third quartiles, minimum, maximum).
- Pathological complete response (pCR) rate will be summarized using all treated subjects who received surgery by a binomial response rate. The Clopper-Pearson method will be used to estimate the two-sided 95% confidence intervals. Summary of continuous % residual viable tumor (%RVT) results will be provided descriptively if the data is available.

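### The exploratory pCR endpoint is defined per treated subject, but SAP 7.5.3.1 divides by operated subjects, which cannot lower the reported rate and may raise it.

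*SAP*

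**What the plan says.** The texts on pCR do not use one denominator.

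- **Endpoint.** SAP 4.3.1, and Protocol 8.3.3 in the same words: "The proportion of treated subjects who experiences pathologic complete response will be used to determine pathologic response rate of tumors". pCR itself is judged on the complete resected specimen and the sampled regional nodes.
- **Analysis.** SAP 7.5.3.1: "Pathological complete response (pCR) rate will be summarized using all treated subjects who received surgery by a binomial response rate", with a Clopper-Pearson interval.
- **Primary population.** SAP 6.3.2 says of treated subjects: "This is the primary population for efficacy and safety analyses".
- **Objective.** SAP 3.3.1 and Protocol 1.3.3: "To determine pathologic complete response of tumors in subjects who receive surgical resection after two doses of neoadjuvant nivolumab".
- **A further set.** SAP 6.3.2 also defines a pathologic-response-evaluable population: "All treated subject in neoadjuvant cohorts who received study treatment surgery and have known pathological response based on Day 29 TN classification". No analysis section of the SAP names it.
- **Subgroup tables.** SAP 7.9.1.3 gives the pCR rate by PD-L1 status in treated, PD-L1 tested subjects unless specified otherwise. SAP 7.9.2.1 gives it by virus status and names no denominator.

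**The concern.** Whether a subject is operated is settled after nivolumab has started. A subject who progresses, becomes unresectable or has toxicity before surgery drops out of the SAP 7.5.3.1 denominator but stays in the denominator of the defined endpoint. Such cases are foreseeable. SAP 7.5.1.1 plans to summarize reasons for surgical cancellation, if collected. The preoperative ipilimumab bladder cancer trial described in Protocol 1.1.3 had one cancellation for progression among 12 patients. In the gynecologic cohort some subjects go without resection by plan: Protocol 3.1.2 provides that "biopsy followed by chemotherapy/radiation (where appropriate for Gyn patients only) will occur on Day 29".

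At stake is how a reported pCR rate is read. Cohorts are small, so each excluded subject moves the rate visibly and always in the same direction. The overall pCR table may also fail to reconcile with the subgroup tables.

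**Working it through.** **The plan's own figure.** SAP 5 says "Assuming 10%, 15%, and 20% for pathologic complete response rate", and gives more than 89%, 97% and 99% probability of at least one pCR in 21 subjects. From 1 - (1 - p)^21:

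- p = 10%: 89.06%
- p = 15%: 96.71%
- p = 20%: 99.08%

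These reproduce to rounding, although 96.7% is not strictly more than 97%. The 21 here are evaluable subjects, which SAP 6.3.2 defines by paired tissue at screening and Day 29. They are neither all treated subjects nor, in the gynecologic cohort, necessarily operated subjects.

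**Direction.** Let x be the number of pCRs, T the number treated and S the number operated. Every pCR needs a resected specimen, so all x lie within S, and S ≤ T. Then

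x/S = (x/T) × (T/S) ≥ x/T.

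The two are equal only if S = T or x = 0.

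**Size, SCCHN and Merkel cell carcinoma.** By Protocol 3.1.2 and 3.3.1 the post-treatment sample in these tumor types is the operative specimen. If the target of 21 evaluable is met, about 21 are operated and at least 21 are treated. Assume S = 21, x = 3 and T from 22 to 25:

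- operated-only: 3/21 = 14.3%
- all treated: 3/22 = 13.6% to 3/25 = 12.0%
- gap: 0.6 to 2.3 percentage points (T/S = 1.05 to 1.19)

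**Size, gynecologic cohort or an accrual shortfall.** The Day 29 sample may be a core biopsy in the gynecologic cohort, so 21 evaluable subjects can include unoperated ones. Assume T = 21, x = 3 and S from 19 down to 15:

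| Denominator | Rate | 95% Clopper-Pearson |
|---|---|---|
| 21 treated | 14.3% | 3.0 to 36.3 |
| 19 operated | 15.8% | 3.4 to 39.6 |
| 17 operated | 17.6% | 3.8 to 43.4 |
| 15 operated | 20.0% | 4.3 to 48.1 |

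At S = 15 the factor is 21/15 = 1.40. The intervals overlap heavily, so this is a one-directional shift inside wide uncertainty.

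**Reconciliation.** Suppose 25 are treated, all are PD-L1 tested and 21 are operated. Read literally, the PD-L1 pCR tables in SAP 7.9.1.3 have denominators summing to 25, while the overall table in SAP 7.5.3.1 has 21.

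**The case against.** The best case for SAP 7.5.3.1 is that it answers the stated objective, which concerns resected subjects, and that pCR is meaningful only where there is a specimen. On that view, rewording the endpoint to match the objective would resolve the mismatch equally well. An all-treated rate in the gynecologic cohort counts subjects sent by plan to chemoradiation as failures, so it partly measures planned modality. SAP 7.5.3.1 also states its denominator openly, and treated counts are reported under SAP 7.3.1, so a reader could recompute the other rate.

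Much of this stands. It is why the operated-only rate should be kept and why the severity is low. It does not remove the inconsistency. The endpoint is defined per treated subject in both documents, and the SAP names treated subjects as its primary efficacy population. Aligning the endpoint to the objective would mean changing the Protocol as well as the SAP, and it would leave the headline rate conditioned on a post-treatment event.

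Two smaller objections also carry weight. SAP 7.1 says that, where no missing category is shown, "only those subjects with non-missing values for the parameter being assessed are included in the percentage calculation". That could be thought to remove operated subjects with unknown pathology, but a specific denominator normally governs over a general tabulation rule, so this is only a reason to state the handling. The pathologic-response-evaluable set may also be used in table mock-ups in the Data Presentation Plan, which is not available here. What can be said is that SAP Section 7 does not name it.

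**Conclusion.** The mismatch between endpoint and analysis is real, and nothing in the documents reconciles it. The operated-only rate cannot be below the rate that the endpoint defines. With assumed counts, the difference is about 0.6 to 2.3 points in SCCHN and Merkel cell carcinoma if the evaluable target is met. It may reach several points in the gynecologic cohort or after an accrual shortfall (14.3% against 20.0% at 15 operated of 21). It is zero if every treated subject is operated or no pCR occurs.

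A reader might infer more than this in two ways. One is that 21 is the treated count in every tumor type, with clearly fewer operated. The documents do not support that: 21 is an evaluable count, and outside the gynecologic cohort an evaluable subject is by plan an operated one. The other is that the choice of denominator moves the result from one of the plan's assumed pCR levels to the next. Those levels are applied to 21 evaluable subjects, so comparing them with an all-treated rate mixes denominators.

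Severity is low. pCR is exploratory with no decision rule, and no primary or secondary conclusion depends on it.

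**What to change.** In SAP 7.5.3.1:

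- Report pCR in all treated subjects, as the endpoint defines it, counting subjects not operated and those with unknown pathology as no pCR.
- Show beside it the operated-only rate with the number operated, labelled as the analysis that matches the objective.
- For the gynecologic cohort, also state the number not planned for resection, if this was recorded.

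Use the same denominators in SAP 7.9.1.3 and 7.9.2.1. Assign the pathologic-response-evaluable set to the supplementary table, or delete it.

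The cost is SAP wording and one or two extra displays. The two rates need no new data; the gynecologic count depends on whether planned treatment was recorded. The downside is a slightly lower headline rate and, in the gynecologic cohort, an all-treated rate that partly reflects planned modality. Showing both rates with their counts lets the reader see that.

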7.5.3.2 Metastatic Cohorts only

- Change in EBV DNA levels in subjects with EBV positive gastric cancer (monotherapy only) and nasopharyngeal carcinoma will be summarized using descriptive statistics (n, mean, standard deviation, median, first and third quartiles, minimum, maximum).

7.5.4 Interim Analyses

Under the circumstance that data of some tumor types mature faster than others or a strong signal is observed in some tumor types, interim analyses may be performed prior to the completion of

the study in order to facilitate program decisions and to support presentations or publication. These interim analyses will not impact the study duration and the trial will continue as planned.

7.6 Safety

For all safety related analyses, refer to the Core Safety SAP⁶. Safety will be summarized for: all treated, by tumor type; all dose escalation subjects, by tumor type.

7.6.1 Deaths

See Core Safety SAP.

7.6.2 Serious Adverse Events

See Core Safety SAP.

7.6.3 Adverse Events Leading to Discontinuation of Study Therapy

See Core Safety SAP.

7.6.4 Adverse Events Leading to Dose Delay of Study Therapy

See Core Safety SAP.

7.6.5 Adverse Events

See Core Safety SAP.

7.6.6 Select Adverse Events

See Core Safety SAP.

7.6.7 Immune Modulating Medication

See Core Safety SAP.

7.6.8 Multiple Events

See Core Safety SAP.

7.6.9 Clinical Laboratory Evaluations

7.6.9.1 Hematology

See Core Safety SAP.

7.6.9.2 Serum Chemistry

See Core Safety SAP.

7.6.10 Immunogenicity

Immunogenicity data generated from this study may be combined with data from other studies to further explore the incidence of immunogenicity following administration of nivolumab as monotherapy or in combination with ipilimumab, relatlimab or daratumumab. Selected serum samples may be analyzed by an exploratory method that measures anti-nivolumab, anti-ipilimumab, anti-BMS-986016 (relatlimab), or anti-daratumumab antibodies. Please also see [section 7.8](#). These analyses, if conducted, will be reported separately. Immunogenicity will be

reported for anti-drug antibody (ADA) positive status (such as persistent positive, neutralizing positive, only last sample positive, baseline positive and other positive) and ADA negative status, relative to baseline, by cohort and treatment, if applicable. Further details on immunogenicity background and rationale, definitions, population for analyses and endpoints are described in Core Safety SAP.

7.6.11 Vital Signs and Pulse Oximetry

See Core Safety SAP.

7.7 Pregnancy

See Core Safety SAP.

7.8 Pharmacokinetics

The nivolumab, ipilimumab, relatlimab, or daratumumab concentration data obtained in this study may be combined with data from other studies in the clinical development program to develop a population PK model. This model may be used to evaluate the effects of intrinsic and extrinsic covariates on the PK of respective drug. Immunogenicity data generated from this study may also be added as one of the covariates of the model. In addition, exposure-response analyses with selected efficacy and safety endpoints may be conducted. Results of population PK and exposure response-analyses, if conducted using the concentration data (for nivolumab, ipilimumab, relatlimab, or daratumumab) from this study, will be reported separately.

7.9 Biomarkers

Analyses for PD-L1 and virus status are described below. Methodology for biomarkers other than PD-L1 and virus status will be detailed in a separate biomarker SAP.

7.9.1 PD-L1 Expression at baseline subgroups

The following PD-L1 expression subgroups will be considered by tumor type.

For TPS:

- Each baseline quantifiable PD-L1 expression status subgroup:
 - PD-L1 \geq X%
 - PD-L1 $<$ X%
 - Where X% is predefined as 1% and 5% if not otherwise specified.
- Baseline PD-L1 expression not evaluable or indeterminate subgroup.
- Baseline PD-L1 expression not reported.

For CPS:

- Each baseline quantifiable CPS status subgroup:
 - CPS \geq X
 - CPS $<$ X
 - Where X is predefined as 1 and 10 if not otherwise specified.
- Baseline CPS not evaluable or indeterminate subgroup.

- Baseline CPS not reported.

